Title: Zonisamide Treatment of Alcohol Use Disorder: an Evaluation of Efficacy and Mechanism of Action

NCT #: NCT02900352

Document date: June 5, 2020

Document Type: Protocol and Statistical Analysis Plan

1. Principal Investigator: [name]., M.S.

2. Project Title:

"Zonisamide treatment of Alcohol Use Disorder: an evaluation of efficacy and mechanism of action"

3. Purpose, hypothesis and key questions

Purpose: To comprehensively evaluate the efficacy of an anticonvulsant medication zonisamide (ZNS) for the treatment of alcohol dependence in civilians. We want to see if the medication works to reduce harmful drinking patterns, and try to determine whether medication response can be predicted by a few key factors such as genotype, the age of onset of alcoholism (early vs. late), or stress-reactivity. This protocol also contains translational substudies that will help elucidate the mechanism of action of the medication and determine subject characteristics that predict preferential response.

SPECIFIC AIMS: Zonisamide (ZNS) is an anticonvulsant medication for which evidence of efficacy in treating alcohol use disorders (AUDs) was obtained in two small placebo-controlled pilot studies. We propose to 1) add a civilian arm (N=160) to complement the existing VA/CSR&D study comparing ZNS to placebo over 16 weeks of treatment; 2) add important mechanistic and translational components to both trials (potential N=320) to elucidate the mechanism of action of ZNS and enhance our understanding of how anticonvulsant treatments reduce drinking. Importantly, there is no overlap between the VA/CSR&D funding, and the proposed NIH funding. So we will evaluate *efficacy*, *safety*, *and mechanism of action* of zonisamide in treating alcoholism.

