Specific Aim 1) To evaluate fully the efficacy of and scope of effectiveness for ZNS in treating AUDs by adding a civilian arm (*N*=160 randomized, 80 on ZNS and 80 on placebo) to the CSR&D-funded study in veterans, using the same primary outcome (drinks per week) and secondary measures of drinking behavior as the veteran arm [i.e., heavy drinking days/week, percentage of subjects with no heavy drinking days (PSNHDD), craving, reductions in GGT]. Subjects will meet criteria for an AUD (DSM-5) and be heavy drinkers similar to the participants in the VA study. We hypothesize that ZNS will produce a significantly greater reduction in drinks per week than placebo (primary outcome alpha = .05). We also hypothesize that ZNS will significantly improve secondary measures of drinking (corrected for multiple comparisons). We will recruit civilians from the University of Connecticut Health Center (UCHC) and VCU's Institute for Drug and Alcohol Studies (IDAS)

Specific Aim 2) To use telephone-based daily process data collection to elucidate the mechanism of action of ZNS as it relates to changes in craving, anxiety, and genetic variation. This method has been shown to elucidate the mechanism of action of topiramate, as well as its pharmacogenetic interactions. We hypothesize that ZNS' effects will be moderated by genetic variation, craving, and anxiety, but mediated through changes in self-efficacy to reduce heavy drinking.

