6.K.2 Secondary outcome measures: We will use a mixed models approach to examine for a statistically significant difference on heavy drinking days (HDD) per week, changes in GGTP level, measures of alcohol urge/craving (AUQ), and alcohol-related problems (as measured on the SIP). For each of these outcome measures, the model will include fixed effects for medication group, week, and the interaction between medication and week. We will include pre-treatment drinking behavior (past month HDD) as a covariate and will select the best-fitting variance-covariance structure based on Schwartz-Bayesian Information criterion (BIC). We will incorporate a grace period corresponding to the time it takes to titrate the medication to target dose into the models, and we will focus the primary analysis on the 8 weeks of treatment at the target dose. We will use the Hommel's correction for multiple comparisons on the secondary outcomes to guard against chance findings. With last secondary outcome measure percentage of subjects with no heavy drinking days (PSNHDD), we will use a logistic regression analysis with PSNHDD as a categorical dependent variable. Medication condition (PLC or ZNS) will be the main independent variable, and we will include the variables of civilian or veteran status. and sex as covariates. We will also examine the use of biomarkers (GGT, PEth) to verify and adjust subjective drinking data as these biomarkers can detect occult harmful drinking when a subject is not forthcoming.

6. K. 3. Dropouts and missing data: For the analysis of PSNHDD using logistic regression, all dropouts will be counted as relapsed. For all repeated measures analysis, we will use all V.6 05Jun2020

available data on individuals and thus dropouts provide data until the point of dropout. We will compare dropout patterns between groups and if there are concerns of informative dropout and/or informative intermittent missing data, we will use pattern mixture models [98] to perform sensitivity analyses to our main analyses. Adherence to the medication will be evaluated and controlled for in secondary analyses. We will evaluate and compare both medication conditions (PLC, ZNS) for percentage of prescribed pills taken.

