- **6.K. 6. Safety:** Safety will be analyzed using categorical outcomes, defined by the type and severity of adverse effects. Summary measures of adverse events will be developed by organ system from the SAFTEE [77, 78] and will be compared for patients receiving ZNS or PLC using \Box^2 analysis or Fisher's exact tests, with an emphasis on moderate-to-severe adverse events.
- 6. K. 7. Sample Size And Power Estimate (Specific Aim 1): For continuous outcomes, based on the effect sizes from our pilot study of ZNS (showing a moderate effect size on drinks/week d=0.5, and .27 HDD/week), we estimated that a study with N=128 subjects (a 20% drop out rate) would be well powered (>.80) to detect a medium effect size difference on the secondary outcomes HDD per week and total drinks per week for the main effect of group assuming alpha level of 0.05. Based on past trials we are expecting a dropout rate < 30%. We will quantitatively examine the veteran and civilian populations for differences in variance and treatment response, and combine them (if valid) in a patient-level pooled analysis, further increasing power on all outcomes. If substantial differences are observed between the veteran and civilian samples, we will meta-analyze them. For PSNHDD, from the pilot study, in the ZNS group, 12 of 20 subjects did not relapse in the 28 days of the study, compared to 7 of 20 PLC subjects. Using this effect size, the proposed sample size of 80 subjects per group has >89% power to detect such a difference in the rates of no heavy drinking (i.e. 60% vs. 35%), assuming a two-sided alpha level of 0.05. We can also detect slightly smaller differences (60% vs. 38%, 35% vs. 57%) with 80% power under the same assumptions. Both in the estimation of effect

size from the pilot data and in the sample size analysis, dropouts are counted as relapsed to heavy drinking.

6 K. 8. Pharmacogenomic and Micro-longitudinal analyses power estimate (Aim 2, exploratory aims): There is little ZNS-specific data by which we could reasonably estimate effect sizes for these analyses. Three recent treatment studies by our group showed significant pharmacogenetic effects with samples of about 110-150 in each [15, 85, 102]. By using a mixed models approach on drinking variables, and HLM for the micro-longitudinal analyses, we will be adequately powered to detect medium-to-large effects in these analyses.

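### Section 6.K.7 states power for heavy drinking days per week (>.80) and for PSNHDD (>89%) at an uncorrected 0.05, although both are secondary outcomes tested under Hommel; for the civilian sample alone the unadjusted power lies between 0.59 and 0.80 and between 0.73 and 0.89

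*Combined protocol and SAP*

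**What the plan says.** **Power statement (6.K.7).** For the continuous outcomes, N=128 (160 less 20% dropout) "would be well powered (>.80) to detect a medium effect size difference on the secondary outcomes HDD per week and total drinks per week", at alpha 0.05. The pilot effects cited are d=0.5 for drinks per week and .27, with no metric, for heavy drinking days (HDD) per week. For PSNHDD, "80 subjects per group has >89% power to detect such a difference in the rates of no heavy drinking", meaning 60% vs 35% at two-sided 0.05. It adds: "We can also detect slightly smaller differences (60% vs. 38%, 35% vs. 57%) with 80% power under the same assumptions".

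**Testing rule.** Section 6.K.2 says: "We will use the Hommel's correction for multiple comparisons on the secondary outcomes to guard against chance findings". Specific Aim 1 hypothesises that "ZNS will significantly improve secondary measures of drinking (corrected for multiple comparisons".

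**The secondary family.** Section 6.K.2 has five members: HDD/week, GGTP, craving (AUQ), alcohol-related problems (SIP) and PSNHDD. Specific Aim 1 lists four and omits the SIP.

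**The primary.** Specific Aim 1 and 6.K.1.a make drinks per week the primary outcome, at 0.05.

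**Combination with the veteran trial.** For the PSNHDD model, 6.K.2 says "we will include the variables of civilian or veteran status" among the covariates. Section 6.K.7 plans to quantify differences between the two populations and "combine them (if valid) in a patient-level pooled analysis, further increasing power on all outcomes". If they differ substantially, the two samples are to be meta-analysed instead.

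**The concern.** HDD/week and PSNHDD are the two secondaries for which the plan publishes a power figure, and both figures are computed at an alpha that the plan will not, in general, apply to them. Section 6.K.7 does not mention the correction. A reader would take >.80 and >89% as the chance of a significant result under the planned tests in the civilian trial, and under Hommel that chance is lower.

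The dataset behind the PSNHDD figure is also unclear. Its power uses 80 per group, which is the civilian trial, while its model carries a civilian/veteran covariate, which is constant among civilians and has meaning only in combined data.

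The HDD/week sentence has two further faults. It calls drinks per week a secondary outcome. It also claims a basis in the pilot effects, quotes .27 for HDD/week, and then powers a medium effect.

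**Working it through.** **Inputs.** From 6.K.7: d=0.5, N=128 (64 per arm), alpha 0.05, PSNHDD rates, 80 per group. From 6.K.2: Hommel, five secondaries. The alpha for the continuous outcomes has no stated sidedness; two-sided reproduces the figure.

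**Step 1. Reproduce the plan's figures at 0.05.**

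HDD/week, two-sample t-test: noncentrality = d × √(n/2) = 0.5 × √32 = 2.83. Noncentral-t power is 0.801.

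PSNHDD, pooled-variance comparison of proportions: power = Φ{[|p1 − p2| − z·√(2p̄(1 − p̄)/n)] / √([p1(1 − p1) + p2(1 − p2)]/n)}. For 60% vs 35% with n=80, p̄=0.475 and the two standard errors are 0.0790 and 0.0764. So (0.25 − 1.960 × 0.0790)/0.0764 = 1.25, and power is 0.894. The smaller differences give 0.801 (60% vs 38%) and 0.803 (35% vs 57%). All the stated figures reproduce.

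**Step 2. Bound the power under Hommel.** Hommel rejects whenever Bonferroni does (p ≤ 0.05/m) and never rejects when p > 0.05. With m=5, the power for each outcome therefore lies between its power at 0.01 and its power at 0.05, whatever the correlation among outcomes.

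For 60% vs 35% at 0.01: (0.25 − 2.576 × 0.0790)/0.0764 = 0.61, so power is 0.729. For HDD/week, noncentral-t power at 0.01 is 0.585.

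| Civilian sample, unadjusted | 0.01 (m=5 floor) | 0.0125 (m=4 floor) | 0.05 (no correction) |
|---|---|---|---|
| HDD/week, d=0.5, 64 per arm | 0.59 | 0.62 | 0.80 |
| PSNHDD 60% vs 35%, 80 per arm | 0.73 | 0.76 | 0.89 |
| PSNHDD 60% vs 38%, 80 per arm | 0.58 | 0.62 | 0.80 |
| PSNHDD 35% vs 57%, 80 per arm | 0.59 | 0.62 | 0.80 |

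**Step 3. Where in the range?** This depends on the other outcomes, and the plan gives no effect sizes for craving, GGTP or the SIP. Hommel was simulated with 200,000 trials per setting and assumed correlations from 0 to 0.7. If all five outcomes have d=0.5, HDD/week power is about 0.73. If HDD/week alone is affected, power is close to the floor. PSNHDD at 60% vs 35% has about 0.80 to 0.85 if the other four have d=0.5.

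**Step 4. Covariate gain for HDD/week.** Section 6.K.2 adjusts for past-month HDD. With baseline correlation r, the effective effect is d/√(1 − r²). At an assumed r=0.5 this is 0.5/√0.75 = 0.577. With 64 per arm, power is 0.74 at 0.01 and 0.90 at 0.05.

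**Step 5. Pooled data.** The Specific Aims say the project will "add important mechanistic and translational components to both trials (potential N=320", which suggests 320 − 160 = 160 veterans (an assumption). After 20% loss, 320 × 0.80 = 256, or 128 per arm, for HDD/week. PSNHDD keeps 160 per arm because dropouts count as relapsed. At alpha 0.01:

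- HDD/week, d=0.5: 0.919
- PSNHDD 60% vs 35%: 0.975
- PSNHDD 60% vs 38%: 0.918

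**Step 6. The .27.** If it is a standardised difference d, uncorrected HDD/week power is 0.33 with 64 per arm and 0.58 pooled with 128 per arm. If it is a raw difference in days, power cannot be computed from the documents.

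**The case against.** **No figure in 6.K.7 is miscalculated.** It states its alpha both times, and every figure reproduces. That stands. The fault is that the alpha does not match the planned tests.

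**The plan combines the two trials in either case.** It pools if that is valid and meta-analyses if the samples differ. A reader might infer that the shortfall remains unless pooling goes ahead; the documents do not support that, because the fallback is stated. On pooled data the shortfall closes under the assumption of 160 veterans, although a meta-analysis of differing samples may give less. Still, 6.K.7 attaches its figures to N=128 and to 80 per group, which are civilian numbers.

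**The planned HDD/week model is stronger than an unadjusted test.** It adjusts for baseline HDD and uses all available data, including data from dropouts up to the point of leaving. So 0.80 is the upper bound only for an unadjusted comparison of completers, and the corrected range must be labelled that way. But 6.K.7 claims no such gain, and the documents give no correlation from which to compute one.

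**The floors are worst cases, and the family may have four members.** Both true. With four, the floors are 0.62 and 0.76, and the conclusion is the same.

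**Secondaries need no power statement.** The plan chose to publish one, and Specific Aim 1 hypothesises significance after correction. A published figure should describe the planned test.

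**Conclusion.** The point holds for the civilian sample that 6.K.7 uses. The stated >.80 and >89% are nominal. Under Hommel with five secondaries and an unadjusted test, power is bounded by 0.59 and 0.80 for HDD/week at d=0.5, by 0.73 and 0.89 for PSNHDD at 60% vs 35%, and by 0.58 and 0.80 at 60% vs 38%. The bounds need no assumption about correlation; the values inside them (about 0.73 and about 0.80 to 0.85) assume d=0.5 on the other outcomes.

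Two stronger readings are tempting. One is that the trial is underpowered on its primary outcome. It is not affected: drinks per week is tested at 0.05, and 0.80 at d=0.5 with 20% loss is correct. The other is that true HDD/week power is only 0.33. That requires .27 to be d, which the text does not say, and 6.K.7 explicitly powers a medium effect.

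This should be fixed because it misstates the prospects of two named hypotheses. It does not change the design.

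**What to change.** In 6.K.7:

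1. Name drinks per week as the primary outcome, with power 0.80 at d=0.5 and 20% loss.
2. Label the present HDD/week and PSNHDD figures as nominal (uncorrected). Add the Hommel ranges, marked as unadjusted bounds, for the civilian trial alone (0.59–0.80; 0.73–0.89; 0.58–0.80 for 60% vs 38%) and for the data combined with the veteran trial (about 0.92, 0.975 and 0.92 at 0.01 if pooled with 160 veterans). Say that a meta-analysis may give less.
3. Say which dataset the PSNHDD figure describes, in view of the civilian/veteran covariate in 6.K.2.
4. State the metric of the .27 pilot effect. If it is d, give HDD/week power at that effect: 0.33 uncorrected with 64 per arm, 0.58 pooled with 128 per arm.

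Also align the secondary family between Specific Aim 1 (four) and 6.K.2 (five, with the SIP), because Hommel depends on the count.

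The cost is some rewording and a less favourable stated power for two secondaries. The sample size, the primary test and its alpha do not change.

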The potential utility of anticonvulsants to reduce the risk or severity of relapse was demonstrated initially in studies by Mueller et al. [9] and by Brady et al. [10] showing some benefits compared to PLC treatment. Johnson et al. [11] demonstrated the efficacy of topiramate for AD in a double blind, randomized, placebo-controlled trial. In a follow-up, larger (N=371), multi-center, randomized placebo-controlled trial, topiramate was again found superior to PLC with a moderate effect size [12]. A more conservative analysis of the topiramate data, which assumed a return to baseline drinking levels for dropouts, reduced the effect on heavy drinking by about half. Critics have brought attention to the frequency and severity of side effects from topiramate, which limit its effectiveness [12-14]. A recent study showed a moderate dose of topiramate to be fairly well tolerated and efficacious [15]. A placebo-controlled trial of

gabapentin in patients with AD showed significant benefit with the medication, although the dropout rate was high [16].

4.A.2.b. The Rationale For ZNS Treatment Of AUDs:

ZNS is FDA approved for the adjunctive treatment of partial seizures in adults with epilepsy, and widely available as a cheap generic medication. Strong support is available from animal models for the use of ZNS to treat AUDs. Rats chronically administered topiramate or ZNS showed reduced consumption of an ethanol-sucrose solution [17]. Four small clinical trials have examined ZNS effects on alcohol consumption in humans, **one of which was the placebo-controlled pilot study that we recently completed** showing significantly greater improvement with ZNS [18]. Two other clinical trials were open-label [19, 20] and reported findings that agreed with those of our placebo-controlled trial by showing reduced drinking and craving with the medication, plus a favorable safety profile. A small human clinical study of alcohol self-administration and a one-time dose of ZNS in risky drinkers showed a reduction in craving and in the amount of alcohol consumed with ZNS compared to PLC [21]. A trial comparing ZNS to diazepam in treating the alcohol withdrawal syndrome found **ZNS more effective, and ZNS treated subjects had less craving, less anxiety**, and less sedation [22]. In these studies, ZNS was well tolerated, and few participants dropped out.

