either ZNS (80 subjects) or PLC (80 subjects). Note that the translational sub-studies (genetics, and stress reactivity lab) will be performed on both the civilians and veterans, so they will occur at all 4 total sites for both the civilian and veterans studies: VA Connecticut (the West Haven VAMC), UCONN Health Center, VCU IDAS, and the RichmondVAMC. We anticipate an upper limit of enrollment to be N=200, however for the study we have a participant target goal of N=160. For the sake of simplicity, we describe those procedures here written for the civilians only, but they will be added separately to the veterans study protocol also. The funding for the translational sub-studies will come from NIAAA. We would like to reserve the right to enroll veterans here at VCU IDAS for the translational components of the study only, if that is easier logistically than running the translational components at the Richmond VAMC. The Richmond VAMC will recruit veterans for the study, using their specialized protocol and these participants will be given the option of coming to VCU for the add-on stress lab and IVR components.

6.C. Clinical Trial Inclusion and Exclusion Criteria:

Participants: N=160 men and women **civilians** from the greater Richmond area are being recruited through radio, bus, and print advertising, online advertising, study web sites, referrals, and flyers at VCU facilities and community areas (i.e., coffee shops, grocery stores, etc.), as well as surrounding area clinics. We will also utilize HM20000294 in which participants indicated if they would like to be contacted for future studies in order to identify and contact potential participants

Inclusion Criteria (each subject must meet all of the following to participate): a) age 21-70 years, inclusive; b) regular heavy drinkers as defined by averaging ≥ 2 heavy drinking days per week over the 90 days baseline pre-treatment timeline follow-back (TLFB), and *current DSM-5 AUD* that recognize a need to reduce or stop drinking; c) willingness to provide written, informed consent to participate in the study; and d) for women of child-bearing potential (i.e., no hysterectomy, bilateral oophorectomy, or tubal ligation or <2 years postmenopausal), must be non-lactating, practicing a reliable method of birth control, and have a negative serum pregnancy test prior to initiation of treatment. Section 6.I reviews medications allowed and not allowed during study.

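### The >89% power for PSNHDD carries the pilot's success rates over unchanged, so it holds only if this trial's dropout is no higher than the unstated pilot dropout, or if all extra dropouts would have relapsed anyway

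*Combined protocol and SAP*

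**What the plan says.** Section 6.K.7 takes the PSNHDD effect from the pilot, in which "12 of 20 subjects did not relapse in the 28 days of the study, compared to 7 of 20 PLC subjects". It then states that "the proposed sample size of 80 subjects per group has >89% power to detect such a difference in the rates of no heavy drinking", that is 60% against 35% at two-sided 0.05. It adds that 60% against 38% and 57% against 35% are detectable with 80% power. The 80 per group is the full randomised number: section 6.B assigns subjects to "either ZNS (80 subjects) or PLC (80 subjects").

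Three statements on dropout bear on this:

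- For the continuous outcomes, section 6.K.7 allows 20% dropout (160 reduced to 128) and then says "Based on past trials we are expecting a dropout rate < 30" (percent).
- For PSNHDD, section 6.K.3 says that "all dropouts will be counted as relapsed". Section 6.K.7 closes by saying that, in the estimation of effect "size from the pilot data and in the sample size analysis, dropouts are counted as relapsed to heavy drinking".
- On the earlier zonisamide studies, which include the pilot, section 4.A.2.b says: "In these studies, ZNS was well tolerated, and few participants dropped out". No pilot dropout rate is given anywhere.

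**The concern.** When a dropout is a failure by definition, an overall success rate is partly a retention rate. The 60% and 35% contain whatever dropout the pilot had over its 28 days. They contain no allowance for the further dropout that a 16-week trial may have, and 6.K.7 itself plans for 20% and treats 30% as the ceiling.

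The closing sentence of 6.K.7 can be read as having dealt with this. It fixes how dropouts are scored, but it adds nothing for a dropout rate above the pilot's.

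At stake is how a named secondary outcome is read. A null PSNHDD result would be set against a stated power above 89% that depends on an undisclosed retention assumption. The point is separate from any difference in the length of the observation window: it would apply even if the pilot and trial windows were the same.

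**Working it through.** **Inputs from the documents.** Pilot rates 12/20 = 0.60 and 7/20 = 0.35, n = 80 per arm, two-sided 0.05, dropout scored as relapse, trial dropout 20% (planning value) and 30% (upper bound).

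**Inputs that must be assumed.** The pilot's dropout q0, with *few* taken as 0-10%; equal dropout in both arms; and the relation between dropout and relapse.

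**Formula (pooled variance under the null).** With Δ = p1 − p2 and p̄ = (p1 + p2)/2:

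power = Φ{ [Δ − 1.96·√(2p̄(1 − p̄)/n)] / √([p1(1 − p1) + p2(1 − p2)]/n) }

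**Step 1: reproduce the plan.** Δ = 0.25 and p̄ = 0.475. The null standard error is √(2 × 0.475 × 0.525/80) = 0.0790. The alternative standard error is √((0.24 + 0.2275)/80) = 0.0764. So (0.25 − 1.96 × 0.0790)/0.0764 = 1.25 and power = 0.894. The detectable differences also reproduce: 0.801 for 60 v 38 and 0.803 for 57 v 35. The plan's figures are thus obtained from the raw pilot rates with no adjustment.

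**Step 2: what 60% and 35% require under the trial's dropout.** With dropouts scored as failures, the rate needed among retained patients is the overall rate divided by (1 − dropout):

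- Zonisamide: 0.60/0.80 = 75% at 20% dropout, 0.60/0.70 = 86% at 30%.
- Placebo: 0.35/0.80 = 44% at 20%, 0.35/0.70 = 50% at 30%.

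**Step 3: dropout unrelated to outcome.** Pilot dropouts are already failures in the 60% and 35%, so only the excess is removed. Both rates are multiplied by (1 − q1)/(1 − q0), where q1 is trial dropout, and n stays at 80 per arm.

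| Assumed pilot dropout | Trial dropout 20%: rates, power | Trial dropout 30%: rates, power |
|---|---|---|
| 0% | 48.0% v 28.0%, 0.745 | 42.0% v 24.5%, 0.654 |
| 5% | 50.5% v 29.5%, 0.781 | 44.2% v 25.8%, 0.689 |
| 10% | 53.3% v 31.1%, 0.818 | 46.7% v 27.2%, 0.726 |
| 20% | 60.0% v 35.0%, 0.894 | 52.5% v 30.6%, 0.808 |

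**Step 4: dropout related to outcome (pilot dropout 0%).** Suppose the dropouts would have succeeded at only half the pilot rate, so that half of the dropout displaces would-be successes.

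- At 20% dropout, the rates are multiplied by 1 − 0.10: 54% v 31.5%, power 0.83.
- At 30%, they are multiplied by 1 − 0.15: 51% v 29.75%, power 0.79.
- If all extra dropouts would have relapsed anyway, the rates stay at 60% v 35% and power stays at 0.894.

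**The case against.** The strongest reply is that nothing is miscalculated: the power follows from its inputs, and pilot dropouts are already counted as relapsed in the 60% and 35%. That is correct, and it limits the point in several ways.

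- A reader might infer that the plan's own figures give a power of 0.65-0.75. They do not. That range needs zero pilot dropout and dropout unrelated to relapse, and the documents state neither. Its lower end also uses 30%, which the plan gives only as an upper bound. Treating 60% and 35% as rates among completers would count any pilot dropout twice.
- A reader might infer that the section contradicts itself because it discounts 160 to 128 for the continuous outcomes but keeps 80 per arm here. It does not. The mixed models lose information after dropout, whereas under the relapse rule every randomised patient has an outcome, so 80 per arm is the right denominator.
- The evidence on pilot retention is one qualitative sentence closing a paragraph on several studies, some of them open-label and one using a single dose.
- Section 6.K.1.a follows patients whether or not they stay on medication, and dropout is not defined as stopping medication or as loss of assessment. How many patients would be scored as relapsed is therefore uncertain.
- Section 6.K.7 also plans to pool with the veteran trial if valid. With 160 per arm, assuming the potential N = 320 is reached, the same formula gives 0.96 for 48% v 28% and 0.92 for 42% v 24.5%. The shortfall concerns the civilian trial alone, which is the trial to which the >89% refers.

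What remains is that the plan neither states nor justifies the retention assumption on which the printed figure depends.

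**Conclusion.** The point holds as a matter of an unstated assumption, not as an arithmetic error. For the civilian trial alone, >89% is the favourable limit among scenarios in which trial dropout is at or above the pilot's. It is reached only if the two dropout rates match or if all extra dropouts would have relapsed anyway.

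With pilot dropout of 0-10%, equal dropout in both arms and dropout unrelated to outcome, power is about 0.75-0.82 at 20% dropout and 0.65-0.73 at 30%. If only half of the dropout displaces would-be successes and pilot dropout was 0%, it is about 0.83 and 0.79. Across these assumptions the span is about 0.65-0.89, and the documents do not allow it to be narrowed. The stated detectable differences start at 0.80 and rest on the same assumption, with no margin.

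The outcome is secondary and the remedy is small, so this is a correction that should be made rather than a threat to the trial's main conclusion.

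**What to change.** In section 6.K.7:

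1. State the pilot's dropout rate by arm, so that the part already contained in 60% and 35% is visible.
2. State the assumed relation between dropout and relapse.
3. Replace the single figure with a range at 20% and 30% dropout, with dropouts scored as relapsed and 80 per arm kept as the denominator. Until the pilot rate is inserted, suitable wording would be: *for the civilian trial alone, power is 0.89 if dropout matches the pilot's or all additional dropouts would have relapsed; if pilot dropout was 0-10% and dropout is equal in both arms and unrelated to outcome, it is about 0.75-0.82 at 20% dropout and 0.65-0.73 at 30%.*
4. Put the same caveat on the 60% v 38% and 57% v 35% detectable differences.

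The cost is one look-up, one recalculation and a few sentences. The stated power becomes less favourable. Enrolment, the dropout rule and the logistic regression are unchanged, and the 128 used for the continuous outcomes should not be carried over to PSNHDD.
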